#### 7. REGULATORY AND REPORTING REQUIREMENTS:

Adverse event reporting will be as per the current NCI criteria and the MDACC Leukemia-specific Adverse Event Recording Reporting Guidelines. The descriptions and grading scales found in the revised NCI Common Terminology Criteria for Adverse Events (CTCAE) version 4.0 will be utilized for adverse event reporting. (http://ctep.cancer.gov/reporting/ctc.html).

# Serious Adverse Event Reporting (SAE)

An adverse event or suspected adverse reaction is considered "serious" if, in the view of either the investigator or the sponsor, it results in any of the following outcomes:

- Death
- A life-threatening adverse drug experience any adverse experience that places the
  patient, in the view of the initial reporter, at immediate risk of death from the adverse
  experience as it occurred. It does not include an adverse experience that, had it occurred
  in a more severe form, might have caused death.
- Inpatient hospitalization or prolongation of existing hospitalization, unless for planned, elective procedure
- A persistent or significant incapacity or substantial disruption of the ability to conduct normal life functions.
- A congenital anomaly/birth defect.

Important medical events that may not result in death, be life-threatening, or require hospitalization may be considered a serious adverse drug experience when, based upon appropriate medical judgment, they may jeopardize the patient or subject and may require medical or surgical intervention to prevent one of the outcomes listed in this definition. Examples of such medical events include allergic bronchospasm requiring intensive treatment in an emergency room or at home, blood dyscrasias or convulsions that do not result in inpatient hospitalization, or the development of drug dependency or drug abuse (21 CFR 312.32).

- Important medical events as defined above, may also be considered serious adverse events. Any important medical event can and should be reported as an SAE if deemed appropriate by the Principal Investigator or the IND Sponsor, IND Office.
- All events occurring during the conduct of a protocol and meeting the definition of a SAE must be reported to the IRB in accordance with the timeframes and procedures outlined in "The University of Texas M. D. Anderson Cancer Center Institutional Review Board Policy for Investigators on Reporting Unanticipated Adverse Events for Drugs and Devices". Unless stated otherwise in the protocol, all SAEs, expected or unexpected, must be reported to the IND Office, regardless of attribution (within 5 working days of knowledge of the event).
- All life-threatening or fatal events, that are unexpected, and related to the study drug, must have a written report submitted within 24 hours (next working day) of knowledge of the event to the Safety Project Manager in the IND Office.
- Unless otherwise noted, the electronic SAE application (eSAE) will be utilized for safety reporting to the IND Office and MDACC IRB.
- Serious adverse events will be captured from the time of the first protocol-specific intervention, until 30 days after the last dose of drug, unless the participant withdraws consent. Serious adverse events must be followed until clinical recovery is complete and laboratory tests have returned to baseline, progression of the event has stabilized, or there has been acceptable resolution of the event.
- Additionally, any serious adverse events that occur after the 30 day time period that are related to the study treatment must be reported to the IND Office. This may include the development of a secondary malignancy.

## Reporting to FDA:

 Serious adverse events will be forwarded to FDA by the IND Sponsor (Safety Project Manager IND Office) according to 21 CFR 312.32.

It is the responsibility of the PI and the research team to ensure serious adverse events are reported according to the Code of Federal Regulations, Good Clinical Practices, the protocol guidelines, the sponsor's guidelines, and Institutional Review Board policy.

Leukemia Guidelines for AE reporting will be followed.

Adverse Events and Protocol specific data will be entered into PDMS/CORe. PDMS will be used as the electronic case report form.

# 7.1. Expedited Adverse Event Reporting

Leukemia associated symptoms are not to be reported as adverse events on this protocol. Myelosuppression and associated complication are expected events during leukemia therapy and are part of the treatment success (marrow emptying of leukemia cells). Therefore, myelosuppression and associated complications such as fever, infections, bleeding, and related hospitalization will be reported in the study summary.

For this protocol, the following adverse events are specifically excluded from expedited AE reporting:

CTCAE			Hospitalization/	
Category	Adverse Event	Grade	Prolongation of	Comments
			Hospitalization	
	Hemoglobin,			Do not require
Blood/	leukocytes (total	1-4	Yes	expedited
Bone	WBC), lymphopenia,			reporting
marrow/	Neutrophils/			
Infection	granulocytes			
	(ANC/AGC),			
	Platelets, fever,			
	sepsis			
				Hospitalization
Gastro-	Diarrhea, nausea,	1-3	Yes	for grade 3 AEs
intestinal	vomiting, stomatitis			does not
				require
				expedited
				reporting
				Do not
Metabolic/	↓K,↓Mg, ↓Na,	1-4	Yes	require
laboratory	↓glucose, ↑K, ↑Mg,			expedited
	↑glucose, ↑uric			reporting
	acid,↑LDH			unless
	Or other metoablic			hospitalized
	indeces			for

				management
--	--	--	--	------------

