#### 1. OBJECTIVES

The main objective of this study is to collect long term safety and tolerability data in patients with myelofibrosis previously treated with ruxolitinib on protocol 2007-0169.

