#### 2. BACKGROUND

Ruxolitinib (INCB018424 phosphate, JAKAFI™) is an inhibitor of the Janus kinase family of protein tyrosine kinases (JAKs). Ruxolitinib was approved in November 2011 for the treatment of patients with intermediate or high-risk myelofibrosis, including primary myelofibrosis, post-polycythemia vera myelofibrosis and post-essential thrombocythemia myelofibrosis. Ruxolitinib was approved in December 2014 for the treatment of patients with polycythemia vera who have an inadequate response to or cannot tolerate hydroxyurea.

JAKs play an important role in signal transduction following cytokine and growth factor binding to their receptors. In addition, JAKs activate a number of downstream pathways implicated in the proliferation and survival of malignant cells including the STATs (signal transducers and activators of transcription), a family of important latent transcription factors. Aberrant activation of JAKs has been associated with increased malignant cell proliferation and survival. In particular, a causal role for JAK2 has recently been suggested for the majority of patients with Philadelphia chromosome negative MPD.

The MPDs are a group of clonal hematologic diseases that include polycythemia vera (PV), essential thrombocythemia (ET), primary myelofibrosis (PMF) and post polycythemia vera/essential thrombocythemia myelofibrosis (post-PV/ET MF). MF may occur as a primary disorder or it may follow a preceding disease course with PV or ET. The clinical course in this disease is characterized by bone marrow fibrosis, hepatosplenomegaly, progressive anemia, extra medullary hematopoiesis, leukoerythroblastic peripheral blood findings and constitutional symptoms. Overall median survival is 5 years and causes of premature death include leukemic transformation, infections, thrombosis, cardiac failure, hepatic failure, respiratory failure and portal hypertension. For a small subset of patients who are young, otherwise healthy and have a histocompatible donor, allogeneic stem cell transplantation may provide a curative option, although a risk of significant mortality is associated with the procedure.

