#### 2.1 Rationale

Ruxolitinib is an inhibitor of the Janus kinases (JAKs) and is the only approved therapy for patients with myelofibrosis. Protocol 2007-0169 was a phase 1-2 study of ruxolitinib in these patients; now the therapy is approved and the protocol is closing. However, we plan to continue to monitor patients for long term safety and survival.

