  - i) Progressive splenomegaly that is defined by the appearance of a previously absent splenomegaly that is palpable at > 5 cm below the left costal margin or  $a \ge 100\%$  increase in palpable distance for baseline splenomegaly of 5-10 cm or  $a \ge 50\%$  increase in palpable distance for baseline splenomegaly of > 10 cm.
  - ii) Leukemic transformation confirmed by a bone marrow blast count of  $\geq$  20%. iii) An increase in peripheral blood blast percentage to  $\geq$  20% that lasts for  $\geq$  8 weeks.
- 5. **Stable disease:** None of the above.
- 6. **Relapse:** Loss CR, PR, and CI. In other words, a patient with CR or PR is considered to have undergone relapse when he or she no longer fulfils the criteria for even CI.

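### Section 7.1 excludes an undefined class of leukemia-associated symptoms from adverse event reporting in a myelofibrosis safety study, so the incidence tabulated in 8.3 may be too low

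*Combined protocol and SAP*

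**What the plan says.** Section 1 gives the purpose: "The main objective of this study is to collect long term safety and tolerability data in patients with myelofibrosis previously treated with ruxolitinib". Section 2.1 adds that "we plan to continue to monitor patients for long term safety and survival".

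Section 7.1, headed as expedited reporting, opens with "Leukemia associated symptoms are not to be reported as adverse events on this protocol". It continues: "Myelosuppression and associated complication are expected events during leukemia therapy and are part of the treatment success". Complications of myelosuppression (fever, infection, bleeding and the hospital stays they cause) are then assigned to a study summary. Only after that comes a table of events exempt from expedited reporting.

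Section 7 says that adverse events are reported under NCI criteria and the institution's leukemia-specific guidelines. The FDA reporting paragraph refers to the leukemia guidelines again. Section 8.3 tabulates the incidence of adverse events and of treatment-related adverse events.

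**The concern.** Adverse event incidence is the central output of a study whose one stated main objective is long-term safety and tolerability. Section 7.1 lets site staff leave out symptoms they attribute to leukemia, with no definition of which symptoms those are. Section 2 says of this disease that "causes of premature death include leukemic transformation", and puts transformation first in that list. The subjects whose symptoms are most likely to be left out are therefore among the sickest. A symptom not recorded when it occurs may not be recoverable later. Section 8.3 has a conservative default, under which an event with no stated relationship counts as treatment-related, but it cannot act on an event that was never entered.

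**Working it through.** No arithmetic applies. The documents give no transformation rate, sample size or expected event count. The check sets the relevant sections side by side.

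1. **Scope of the sentence.** The table in 7.1 exempts listed events from expedited reporting, which concerns speed and route. The opening sentence says something different: the symptoms are not reported as adverse events. On its wording it is a recording rule, wider than the heading above it.

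2. **Whom it can affect.** Section 3.1 admits subjects still on study 2007-0169, which Section 2.1 describes as a myelofibrosis study. Section 3.2 lists no exclusions, so the absence of leukemia at entry is inferred and not stated. On that inference, a leukemia-associated symptom arises either from transformation on study or, if the term is read loosely, from the myelofibrosis. The narrow reading touches few subjects. The loose reading could touch many subjects throughout follow-up.

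3. **Effect on 8.3.** An event not reported as an adverse event is not counted. The denominator in 8.1 (dosed, with at least one follow-up safety assessment) does not change. Incidence can therefore only fall or stay the same.

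4. **Other routes by which the information could reach the results.**

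| Route | What it captures | Summarised in Section 8? |
|---|---|---|
| Response assessment (Sections 5.1, 5.2, 6), every 6 cycles and at end of study | Progressive disease, including "Leukemic transformation confirmed by a bone marrow blast count of" at least 20% | No. The contents page lists an efficacy analysis, but the body of Section 8 has none |
| Serious events to the IRB (Section 7) | Every event meeting the seriousness definition | No separate summary |
| Serious events to the IND Office (Section 7) | All serious events whatever the attribution, unless the protocol provides otherwise; 7.1 could be read as providing otherwise | No separate summary |
| Late related serious events (Section 7) | Related events beyond 30 days: "This may include the development of a secondary malignancy" | No |
| Study summary (Section 7.1) | Myelosuppression and its complications | Not defined and not linked to 8.3 |
| Laboratory shift tables (Section 8.4) | Abnormal laboratory values | Yes, but these are not symptoms |

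5. **What remains.** Non-serious symptoms put down to leukemia have no route into any planned safety table. Serious ones have a reporting route, but not a clear path into 8.3. Section 7 also defines seriousness as a property of an adverse event or suspected adverse reaction. A symptom already declared not to be an adverse event might not be put to that test.

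**The case against.** The strongest reply is that little is truly lost. The sentence speaks of symptoms and never mentions transformation, which is graded as progression at regular visits. Deaths, life-threatening events and hospital admissions meet the seriousness definition and must go to the IRB, and that sentence carries no exception clause. Infection and bleeding through myelosuppression are explicitly to be reported somewhere. Sections 4.3 and 5.3 tie continued therapy to absence of progression, and routine capture of serious events stops 30 days after the last dose, so the exposed period after transformation may be short. The leukemia-specific guidelines, which are not among the documents, may define the term. The sentence also reads like wording for leukemia trials carried over, and not like a decision about transformation.

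Most of this stands, and it limits the point. A reader might infer that 7.1 removes the harms of transformation from the study, that transformation survives only as a response grade, or that every symptom of a transformed subject can be dropped. The documents support none of these. The serious event rules and the study summary remain, and drug toxicities or unrelated events in such a subject are not leukemia-associated.

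The reply does not remove the defect. None of these routes is stated to feed the incidence in 8.3, non-serious symptoms fall outside the serious event rules, and a definition held in another document does not make the protocol's own rule clear. Carried-over wording still instructs the sites.

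**Conclusion.** The point holds in this form: 7.1 withholds an undefined class of symptoms from adverse event reporting, in terms that do not fit the study population, and so may bias the incidence in 8.3 downward. The direction follows from the text; the size does not. A reader might be tempted to apply an outside transformation rate to obtain a percentage of subjects affected. The documents give no such rate. The result would also ignore competing deaths and discontinuations and the selection of subjects still benefiting from therapy, and it would count subjects who transform, not events lost.

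The conclusion assumes that sites follow the sentence as written and that the cited leukemia guidelines do not already override it. The lack of any response, progression or survival analysis in Section 8 is a separate gap. The sentence did not cause it, but it means that nothing offsets the loss.

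**What to change.** - Delete the sentence in 7.1. State instead that all adverse events are recorded in PDMS and tabulated in 8.3 whatever their presumed relation to myelofibrosis or leukemia, and that the table in 7.1 limits expedited reporting only.
- State that this prevails over the leukemia-specific guidelines cited in Section 7 wherever they differ.
- Reconcile 7.1 with the serious adverse event rules in Section 7, so that it is clear whether 7.1 counts as an exception to reporting to the IND Office.
- Add to Section 8 a descriptive count of leukemic transformations and a rate per patient-year, dated from the response assessment. Visits are 6 × 28 = 168 days apart, with a 30-day window either way, so the date is approximate unless the date of diagnosis is also entered. Transformation can stay classed as progression and need not be recoded as an adverse event.

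The cost is a wording amendment, some added event entries, one short table and a less favourable incidence figure. No new visit or test is needed.

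### Section 7.1 exempts hospitalized cytopenias, fever and sepsis from expedited reporting on a leukemia rationale that does not fit this myelofibrosis safety study, and leaves the IND Office deadline open

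*Combined protocol and SAP*

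**What the plan says.** Section 7.1 (Expedited Adverse Event Reporting) begins: "Leukemia associated symptoms are not to be reported as adverse events on this protocol". It then gives its reason: "Myelosuppression and associated complication are expected events during leukemia therapy and are part of the treatment success (marrow emptying of leukemia cells". From this it concludes that "myelosuppression and associated complications such as fever, infections, bleeding, and related hospitalization will be reported in the study summary". A table follows, introduced by "For this protocol, the following adverse events are specifically excluded from expedited AE reporting". Its rows are:

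- **Blood/bone marrow/infection:** hemoglobin, leukocytes, lymphopenia, neutrophils/granulocytes, platelets, fever and sepsis; Grade 1-4; hospitalization marked Yes; no expedited report.
- **Gastrointestinal:** diarrhea, nausea, vomiting and stomatitis; Grade 1-3; hospitalization marked Yes; the comment exempts hospitalization for Grade 3 events.
- **Metabolic/laboratory:** electrolytes, glucose, uric acid, LDH and others; Grade 1-4; hospitalization marked Yes; the comment exempts these except when the patient is hospitalized to manage them.

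The SAE part of Section 7 lists among its seriousness criteria "Inpatient hospitalization or prolongation of existing hospitalization, unless for planned, elective procedure". Its general duty reads: "Unless stated otherwise in the protocol, all SAEs, expected or unexpected, must be reported to the IND Office, regardless of attribution (within 5 working days". A faster rule follows: "All life-threatening or fatal events, that are unexpected, and related to the study drug, must have a written report submitted within 24 hours". Section 7 opens with "Adverse event reporting will be as per the current NCI criteria and the MDACC Leukemia-specific Adverse Event Recording Reporting Guidelines", and its FDA part repeats that the leukemia guidelines apply. Those guidelines are not in the documents.

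**The concern.** There are two problems.

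The first is the premise. Section 7.1 treats myelosuppression as evidence that treatment is working, which belongs to remission-induction therapy in leukemia. Here the patients have myelofibrosis, are already taking ruxolitinib and benefiting from it (Section 3.1), and are followed mainly for long-term safety and tolerability (Section 1). A cytopenia in this setting is a toxicity of interest.

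The second is the deadline. A non-elective admission for sepsis or a low platelet count is an SAE under Section 7. Whether it must reach the IND Office within 5 working days depends on what Section 7.1 means by *expedited*, and the protocol does not say. The IND Office is the step that forwards SAEs to FDA. If staff read Section 7.1 as a waiver, serious non-fatal cases of the drug's main toxicities need not reach that office by any stated date, in a study where treatment can continue indefinitely (Section 4.3).

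**Working it through.** The plan states no figure to reproduce. The check sets the sections side by side.

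**Step 1: does the rationale fit the study?**

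- Section 1 gives the population as myelofibrosis and the main objective as long-term safety and tolerability.
- Section 2.3 names the sequelae of decreased hematopoiesis as the primary clinical risks. It lists anemia, thrombocytopenia and neutropenia as the most frequent hematologic reactions, and infection as a risk of myelosuppression.
- Section 4.4 ties mandatory dose decreases to platelet counts for safety reasons.
- Section 7.1 uses the word leukemia 3 times and myelofibrosis 0 times.
- The blood/infection row has 7 event terms. They cover 3 of the 3 reactions that Section 2.3 calls most frequent: hemoglobin for anemia, platelets for thrombocytopenia, neutrophils for neutropenia.

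Section 7.1 thus presents as success what Sections 2.3 and 4.4 treat as harm. The sentence on leukemia-associated symptoms does not fit either. Read literally, it refers to nothing until leukemic transformation, which Section 6 counts as progression. Read as meaning symptoms of the underlying disease, it would bar those symptoms from adverse event reporting. The text does not say which is meant.

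**Step 2: is *expedited* defined?** The word occurs 1 (contents list) + 1 (heading of 7.1) + 1 (exclusion sentence) + 3 (table comments) = 6 times. The contents entry and the heading are the same title. None of the 6 gives a recipient or a deadline, and neither Section 7 deadline is called expedited.

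**Step 3: which deadline applies to a listed event that is serious?** The 5-working-day rule yields to anything the protocol states otherwise, but Sections 7 and 7.1 do not cite each other on this. Two readings are open:

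- Reading A: Section 7.1 is the exception to the 5-working-day rule.
- Reading B: Section 7.1 waives only faster reporting, and the only faster rule in Section 7 is the 24-hour one.

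| Blood/infection event | Reading A | Reading B |
|---|---|---|
| Hospitalized, not fatal, outside the 24-hour criteria | No IND Office deadline stated; study summary, undated | 5 working days |
| Life-threatening, not fatal, unexpected and related | 24-hour rule has no exception clause; effect of 7.1 not stated | Could fall from 24 hours to 5 working days |
| Fatal (Grade 5, in no row) | 5 working days, or 24 hours if unexpected and related | Same |

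Reading B has a further difficulty. Section 7.1 calls these events expected, and the 24-hour rule covers only unexpected ones. If that label governs, the 24-hour rule never reached them and Reading B waives nothing that Section 7 states.

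**Step 4: how far does the hospitalization exemption extend?** The column reads Yes in all 3 rows, but only 2 exempt hospitalized events outright: blood/infection (Grade 1-4) and gastrointestinal (to Grade 3). The metabolic comment restores reporting when the patient is hospitalized for management, so that row's column and comment need reconciling.

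**Step 5: what is untouched?** There is no carve-out in IRB reporting of SAEs, in SAE capture to 30 days after the last dose, in PDMS/CORe entry, or in the tabulation of adverse events in Section 8.3.

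**The case against.** The strongest reply is that this is ordinary drafting. Section 7 sets a general rule that gives way where the protocol states otherwise, and Section 7.1 then names specific exclusions. On that view nothing conflicts. The leukemia guidelines that Section 7 adopts may also define *expedited* and settle the matter. Much of this stands: the text shows an ambiguity, and *undefined* is established only for the protocol as supplied. A reader might infer that Section 7.1 contradicts Section 7. The opening clause of the 5-working-day rule prevents that conclusion. But if the exception is intended, its stated reason is still wrong for this disease, and no guideline on reporting mechanics would repair it.

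A second reply is that the table governs how reports are sent and not what is collected. This also stands. A reader might infer that cytopenias and infections drop out of the safety data set. The documents do not support that, for the reasons in Step 5. Only the sentence on leukemia-associated symptoms could remove data, and its scope is unclear.

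There are further safeguards. The same electronic SAE application serves the IRB and the IND Office. Section 7 holds the investigator to federal regulations, good clinical practice and IRB policy. Section 5.4 asks home physicians to report life-threatening events to the investigator within 24 hours. These reduce the risk, but none sets an IND Office deadline for the listed events.

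**Conclusion.** The concern holds, as an unsuitable rationale joined to an unresolved reporting rule. The point should be fixed, with medium confidence. For a non-fatal hospitalized event in the blood/infection row outside the 24-hour criteria, the IND Office deadline is either 5 working days or none stated. For a life-threatening, unexpected and related event in that row, the 24-hour report could become a 5-working-day one. The effect is mainly on prompt IND Office review and onward reporting to FDA. The number of affected reports cannot be estimated, because the documents give no SAE counts.

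Two broader inferences are not supported. Fatal events are not exempt, since Grade 5 is in no row. Nor do all three rows waive reporting of hospitalized events, given the metabolic comment.

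The conclusion assumes that the protocol text is what staff work from. The unseen leukemia guidelines could resolve the deadline question, but not the mismatch of rationale.

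**What to change.** 1. Delete the leukemia treatment-success rationale from Section 7.1. Delete the sentence on leukemia-associated symptoms, or restate it for myelofibrosis.
2. Reconcile Section 7.1 with the SAE rules in Section 7. Define *expedited* by recipient and deadline. State that a listed event meeting the SAE definition stays under the 5-working-day rule and, where its criteria are met, the 24-hour rule. If the sponsor wants an exception, it should give a myelofibrosis-specific reason and name the alternative route and its date.
3. Align the hospitalization column and the comments of all three rows with that statement.

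The cost is a wording amendment touching all three rows, and possibly more SAE forms, in a number that cannot be estimated from the documents. No visits or procedures are added.
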